9 APPENDICES

9.1 APPENDIX 1: NOTES

- All statistical summaries and analyses will be carried out using SAS Software version 9.2 or higher.
- Where formal statistical tests are performed, significance will be declared using a 2-sided 5% level of significance

PFIZER CONFIDENTIAL

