## 7.7.2. Statistical Considerations

Statistical analyses of safety and effectiveness parameters will be primarily descriptive in nature; no statistical hypotheses will be tested. No imputations for missing data are planned.

As required by MFDS regulations, the periodic report should be submitted to MFDS every 6 months for the first two years and then annual report should be submitted to MFDS for the third, fourth and fifth year. The final report should be submitted in the sixth year. Interim analysis will be performed in time for the report submission.

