#### **7.7.2.2. Effectiveness Analyses**

- The cumulative percent of patients who become pregnant by month 6 will be calculated as  $100*(1 - \text{Kaplan-Meier curve at month 6})$ , where the Kaplan-Meier (KM) method for estimating survival function will be applied to time-to-pregnancy. Patients who did not become pregnant will be censored at the time of their last follow-up. The KM method will also be used to calculate a 95% confidence interval for this cumulative percent at month 6.
- The rate of pregnancies per 100 person-years of follow-up will be accompanied by an 95% confidence interval; this confidence interval will be based on the Poisson distribution.
- Mean change in VAS scores from baseline will be tested against zero change using the paired t-test; p-values  $\leq 0.05$  will indicate statistically significant change. Mean change will also be described using a 95% confidence interval.

Detailed methodology for summary and statistical analyses of data collected in this study will be documented in a SAP, which will be dated, filed and maintained by the sponsor. The SAP may modify the plans outlined in the protocol; any major modifications of primary endpoint definitions or their analyses would be reflected in a protocol amendment.

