4 HYPOTHESES AND DECISION RULES

Not Applicable

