8.2.1.3 Adverse Events by Baseline Characteristics

The following will be presented for AEs, split by the baseline characteristics using the safety analysis set:

[figure not shown]
- The number of subjects to whom AE occurred and the number of AEs will be calculated.
- The proportion of subjects to whom AE occurred and its 95% confidence interval will be estimated and compared between subcategories of each baseline characteristic using a chi-square test or Fisher's exact test. When more than 20% of the expected frequency of the cell count is less than 5, Fisher's exact test will be used instead of the chi-square test.
- Adverse event presentations will be split by the following baseline characteristics: age, purpose of administration, medical history (past/present), concomitant medication, concomitant therapy, total number of injections of Sayana®, dose per injections of Sayana®, paediatric status, geriatric status, kidney disorder, liver disorder (see section 8.2.1.1).

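### The SAP attaches a 5% significance declaration to eleven unadjusted adverse-event subgroup comparisons, although the protocol says no hypotheses are tested and the SAP sets no decision rules

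*SAP*

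**What the plan says.** **Statements that nothing is tested.** Protocol 7.7.2: "Statistical analyses of safety and effectiveness parameters will be primarily descriptive in nature; no statistical hypotheses will be tested". SAP Section 4, headed "HYPOTHESES AND DECISION RULES", has one entry: not applicable.

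**Statements that tests are done.** SAP 8.2.1.3 has the proportion of subjects with an adverse event estimated with a 95% confidence interval and "compared between subcategories of each baseline characteristic using a chi-square test" or Fisher's exact test. Fisher's test replaces chi-square when more than 20% of expected cell counts are below 5. SAP 8.1.2 gives the same rule for categorical data in general. The characteristics are "age, purpose of administration, medical history (past/present), concomitant medication, concomitant therapy, total number of injections of Sayana®, dose per injections of Sayana®, paediatric status", followed by geriatric status, kidney disorder and liver disorder.

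**The threshold.** SAP Appendix 1 says that, where formal tests are performed, "significance will be declared using a 2-sided 5% level of significance".

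**The pain score.** Protocol 7.7.2.2 has a significance test of its own: "Mean change in VAS scores from baseline will be tested against zero change using the paired t-test", with p-values of 0.05 or less called statistically significant. SAP 8.2.2 carries the paired t-test forward, while SAP 8.1.1 rules out formal analysis of continuous data.

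**The concern.** The two documents give the report writer conflicting instructions. Two passages say there are no hypotheses and no decision rules. Two others supply a set of subgroup tests and a rule for calling each result significant. The subgroup tests do not appear among the safety analyses in Protocol 7.7.2.1.

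Followed literally, the re-examination report to the regulator could describe adverse-event proportions as significantly different by age, indication or concomitant medication, with no control of the error rate and no note that the comparisons are exploratory. The study size of 600 is a regulatory minimum (Protocol 7.5) with no power calculation, so a non-significant label would be as poorly supported as a significant one.

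**Working it through.** The documents state no error rate for these comparisons, so there is no figure of the plan's to reproduce.

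**Inputs**
- Number of comparisons: SAP 8.2.1.3 lists 8 characteristics up to paediatric status, then 3 more: 8 + 3 = 11. If past and present medical history are tested separately, 12.
- Level: two-sided 0.05 for each test (SAP Appendix 1).
- Outcome: one, any adverse event (SAP 8.2.1.3).
- Adjustment: none stated.

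**Independent tests, no true differences.** The chance of at least one false declaration among k tests is 1 − 0.95^k, and the expected number is 0.05k.

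| k | Chance of at least one | Expected number |
|---|---|---|
| 7 | 30.2% | 0.35 |
| 8 | 33.7% | 0.40 |
| 9 | 37.0% | 0.45 |
| 11 | 43.1% | 0.55 |
| 12 | 46.0% | 0.60 |
| 14 | 51.2% | 0.70 |

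**Why fewer than eleven count in full**
- Geriatric status (65 or over): post-menopausal women are excluded (Protocol 7.2.2) and eligibility violators leave the safety set (SAP 5.1), so the older stratum should be empty or nearly so.
- Dose per injection: one syringe versus other. Dosage violators leave the safety set, so one level should be nearly empty.
- Liver disorder: significant liver disease is an exclusion, so the group is probably sparse and Fisher's test will be conservative.
- Age group, paediatric status and geriatric status all divide the same variable, so they are not independent.

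Dropping the geriatric and dose comparisons leaves 11 − 2 = 9, hence 37.0% under independence.

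**Simulation of overlap and sparse groups.** There were 1,500 runs with 600 women, no true effects, the SAP's chi-square/Fisher rule, overlapping age splits, and empty geriatric and dose strata. The assumptions, none of which come from the documents, were:
- age: mean 33, SD 8, limited to 16–52;
- 20% in one indication group, 30% with medical history, 30% with concomitant medication, 10% with concomitant therapy;
- injections split 40/35/25 over three levels;
- kidney and liver disorder 1% each.

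| Assumed adverse-event rate | Chance of at least one false declaration |
|---|---|
| 5% | 31.1% |
| 10% | 30.2% |
| 20% | 33.1% |
| 30% | 32.4% |

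About 9 comparisons were testable per run. The simulation error is about √(0.32 × 0.68 / 1500) = 1.2 percentage points, so the four rates are not clearly different. Overlap of kidney and liver disorder with medical history was not modelled and would probably lower the figure a little.

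**Result.** The range is 30% to 43%, or 30/5 = 6 to 43/5 ≈ 9 times the nominal 5%. Bonferroni over eleven tests would need 0.05/11 = 0.0045 per test.

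**The case against.** **The SAP may depart from the protocol.** Protocol 7.7.2.2 allows this and requires an amendment only for major changes to primary endpoints or their analysis. That permits the added tests. It does not resolve the conflict inside the SAP between Section 4 on one side and 8.2.1.3 with Appendix 1 on the other.

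**Section 4 may mean only that there is no confirmatory hypothesis.** This is a fair reading and compatible with nominal p-values. It is harder to square with a rule that declares significance.

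**Appendix 1 does not name the subgroup tests.** True: its sentence is conditional on formal tests being performed. Chi-square and Fisher's tests meet that condition and nothing exempts them, but the link is an inference from reading the sections together.

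**Unadjusted screening suits a surveillance study.** The objectives are to detect and observe reactions, so leaving out a multiplicity adjustment is defensible. This stands, and the point does not ask for one. Screening does not, however, need a significance declaration.

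**The regulator's guideline may require the tests.** Protocol 7.9 says the SAP is governed by it, and the guideline cannot be seen here. The fix keeps every test and changes only what is declared.

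A reader might also draw stronger conclusions that the documents do not support:
- *A false finding is likely.* No count supported by the SAP reaches one half; under independence that takes 14 tests.
- *The plan is purely descriptive.* The protocol says primarily, and it tests the pain score itself. The tension therefore exists within the protocol too.
- *The report will name risk factors.* Neither document says so.

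**Conclusion.** The inconsistency is real and in the current text. The adverse-event subgroup comparisons carry a significance rule that Protocol 7.7.2 and SAP Section 4 do not provide for, with neither adjustment nor an exploratory label.

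With no true differences, the chance of at least one false significant result is about 43% if all eleven comparisons are independent and testable (46% if medical history counts twice). It is more plausibly 30% to 37%. The lower range depends on assumed group shares and event rates and on the geriatric and dose strata being nearly empty. All figures are for one analysis. SAP Section 3 reserves the confidence intervals by baseline characteristic for the final report but does not clearly say whether the tests are also run at interim reports; repetition would raise the risk.

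A separate reason favours a descriptive label over Bonferroni. Concomitant medication includes drugs started after enrolment (Protocol 7.3.1.4), and medication used because of adverse events is itself a safety parameter (Protocol 7.7.1.2). The number of injections depends on how long a woman stays on treatment. An association with either could run from the event to the characteristic, and a stricter threshold would not correct that.

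**What to change.** 1. In SAP 8.2.1.3, add: *P-values for comparisons of adverse-event proportions between baseline subcategories are nominal and descriptive. No statistical significance will be declared from them. The proportions with their 95% confidence intervals are the main presentation.*
2. In SAP Appendix 1, keep the 5% sentence but except the comparisons in 8.2.1.3. Replacing the sentence for all tests would set the SAP against the pain-score test in Protocol 7.7.2.2.
3. Reconcile the pain-score t-test separately. Protocol 7.7.2.2 and SAP 8.2.2 require it, Protocol 7.7.2 says no hypotheses are tested, and SAP 8.1.1 says continuous data get no formal analysis.

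**Cost.** Items 1 and 2 are SAP wording only; no data, estimate, interval or test is lost. Item 3 may need a protocol clarification as well as an SAP edit. The real downside is that adverse-event subgroup differences can no longer be reported as significant. The sponsor should confirm that the regulator's guideline allows the descriptive label.
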